#### **7.2.1.1. Sub-Group Analyses**

The primary efficacy outcome and key secondary outcome will be analyzed for the Per Protocol population. Subjects who withdrew prior to completing 48 hours in the treatment period will be excluded from the PP population. Details will be described in the SAP.

#### **7.2.1.2. Baseline Descriptive Statistics**

Complete demographic and baseline data will be tabulated. The medical history, which will be coded in MedDRA, will be presented. The disease history data, with a focus on the previous treatment and current staging, and the information collected on the procedure to apply the treatment will also be summarized.

#### **7.2.1.3. Concomitant Medication**

All medication taken during the trial will be, at a minimum, listed with the start and stop dates. Concomitant medications will be coded using the World Health Organization (WHO) drug dictionary and summarized by anatomical therapeutic chemical (ATC) level 2 (pharmacological or therapeutic sub-group) and ATC level 4 (chemical sub-group).

#### **7.2.1.4. Interim Analyses**

There are no formal interim analyses planned. Safety and tolerability review will be conducted by the DSMB.

#### **7.2.2. Extent of Exposure**

A summary of exposure to study drug including the total exposure to USB002 and the duration of exposure, will be provided.

### **7.2.3 Safety Analyses**

All subjects who are enrolled and infusion dose of study drug/placebo was started will be included in the descriptive analysis. All safety and tolerability assessments will be based on the safety analysis set, which is defined as all subjects who have been randomized into the study. All subjects will be included in the analyses irrespective of protocol deviations or discontinuation from the study. No formal statistical analysis will be performed on safety data. Part 1 and Part 2 will be presented separately.

#### **7.2.3.1. Adverse Events**

The number of subjects reporting, and number of events reported will be presented in frequency tables (overall, by intensity, by relationship and by outcome) for each dose cohort in each group. AEs of special interest will be presented separately. No specific AEs of interest are prospectively defined for the purposes of this study. AEs will be coded according to MedDRA (Vn. 23.1). All AE and abnormal laboratory variables will be assessed according to the CTCAE v5.0 grading system. Treatment-emergent adverse events (TEAEs) (events not present at baseline and worsened in severity following the start of treatment) will be presented. The following summaries will be provided at a minimum (the SAP will provide further details of summaries that will be provided):

- A summary of the number and percentage of patients reporting any TEAE/SAE;
- A summary of the number and percentage of patients reporting TEAEs according to severity;
- A summary of the number and percentage of patients reporting related TEAEs/SAE;
- A summary of the number and percentage of patients reporting TEAE/SAE by treatment group, preferred term, and system organ class;
- A summary of the number and percentage of patients reporting TEAE/SAE by treatment group, severity, and system organ class;
- A summary of the number and percentage of patients reporting TEAE/SAE by treatment group, by relationship to study drug, and system organ class; and
- A summary of the number and percentage of patients reporting a TEAE leading to withdrawal from study treatment by treatment group, preferred term, and system organ class.

Listings of the above will also be presented for the DSMB reviews on an ongoing basis; for each subject and for each TEAE, the worst severity recorded will be attributed and used in the by-severity summaries.

#### **7.2.3.2. Laboratory Analytes**

Summary statistics (mean, median, standard deviation, minimum, and maximum) and change from baseline to each scheduled study assessment will be presented for all

continuous laboratory parameters. Baseline is defined as the latest non-missing laboratory assessment prior to the first study drug infusion.

For continuous laboratory parameters, shift tables of the number and percentage of patients with normal, low, or high results (as defined by the normal ranges) will be presented from baseline to the most extreme post baseline value by group and treatment group. For categorical urinalysis parameters, shift tables of the number and percentage of patients by classification at baseline and each post baseline visit will be presented. Abnormal laboratory values will be graded according to the latest version of the CTCAE (v5.0). All laboratory assessments will be listed.

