#### 2.1.1 Primary Objectives and Endpoints

The primary objectives of safety and tolerability of USB002 will be evaluated for rate of occurrence and severity of AEs resulting from clinical changes (Visit 1/Day 1 to Day 28): cardiovascular parameters, to include blood pressure (BP), heart rate (HR), 12-lead electrocardiogram (ECG), and requirements for inotropes and vasopressors; laboratory parameters, to include kidney and liver function.

The primary endpoint of preliminary efficacy will be demonstrating the difference between USB002 and placebo groups in time to peripheral capillary oxygen saturation ( $\text{SpO}_2$ )  $\geq 94\%$ , sustained for at least 48 hours, on room air through Day 28.

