#### **4.2. Exclusion Criteria**

1. Terminally ill patients due to underlying cardiac, cancer or severe debilitating neurological disease including coma;
2. Hospitalization expected to be < 96 hours due to medical improvement;
3. Interstitial lung disease;
4. Patients receiving vasopressors at time of starting infusion;
5. Correction of QTc values obtained by 12 lead EKG using Fridericia's formula (QTcF) > 450 ms;
6. History of hypotension (mean arterial blood pressure < 65 mmHg), unrelated to COVID-19 infection;
7. Alanine aminotransferase (ALT) or aspartate aminotransferase (AST) > 3 times upper limit of normal;
8. Creatinine >115umol/L (**Part 2 only**);
9. BUN > 8.3 mmol/L (**Part 2 only**);
10. Participating concurrently on another clinical trial for the experimental treatment of COVID-19;
11. Patients who appear to be showing clinical improvement, in the investigator's opinion (and documented in the source), between screening and baseline (infusion);
12. Active chemotherapy use;
13. Pregnant and/or lactating women.

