### **6.1.1. Definition of Adverse Events (AE)**

An AE is any untoward medical occurrence in a patient or clinical investigation subject administered a pharmaceutical product that which does not necessarily have a causal relationship with this treatment. An AE can therefore be any unfavorable and unintended change in structure, function, sign, or symptom temporally associated with the use of a medicinal product, whether related to the product. Undesirable changes in laboratory values should not be considered AEs unless they are considered symptomatic of a clinical condition or diagnosis, are evaluated as clinically significant, or require therapy. Worsening of a pre-existing condition is also considered an AE, as is the discovery of an abnormal finding during a physical exam (done per SOC) that was not included in the medical history. Clinical conditions attributable to disease progression will be considered AEs.

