8.2.3. Laboratory Assessments

Laboratory assessments with quantitative results, including raw assessments at each visit and change from baseline at post-baseline visits, will be summarized by dose level cohort, and visit for each test.

Each no-missing lab result's normal/abnormal status (e.g., normal/low/high for quantitative results, and normal/abnormal for qualitative results) will be calculated based on the normal reference ranges provided by the lab. The status will be summarized using shift tables from baseline to each post-baseline time point.

All lab data will be presented in by-subject data listing.

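### No laboratory table counts subjects whose kidney or liver tests worsen from an already high baseline, because the shift tables stop at low/normal/high

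*Protocol*

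**What the plan says.** - **Shift tables.** Protocol 7.2.3.2 plans "shift tables of the number and percentage of patients with normal, low, or high results (as defined by the normal ranges", from baseline to the most extreme later value. SAP 8.2.3 assigns each result a status, "normal/low/high for quantitative results, and normal/abnormal for qualitative results", and then: "The status will be summarized using shift tables from baseline to each post-baseline time point".
- **Entry limits (Protocol 4.2).** Exclusion 7 removes "Alanine aminotransferase (ALT) or aspartate aminotransferase (AST) > 3 times upper limit of normal" and applies to both parts. Exclusion 8, "Creatinine >115umol/L", and exclusion 9, on BUN, are marked as applying to Part 2 only. No exclusion concerns bilirubin or alkaline phosphatase.
- **Who is analysed.** SAP Section 2 reports 21 subjects, all in Part 1. SAP 6.1 drops the Part 2 analyses.
- **Importance of these tests.** The primary safety objective (Protocol 2.1.1, repeated in SAP 3.1) names "laboratory parameters, to include kidney and liver function".
- **Other laboratory output.** SAP 8.2.3 summarises raw values and change from baseline by dose cohort and visit, and lists all results by subject. SAP 7.4 gives the statistics as mean, SD, median, range and 95% CI, with no inference.
- **CTCAE grading.** Protocol 7.2.3.1 and 7.2.3.2 say that abnormal laboratory values will be graded by CTCAE v5.0, but specify no table of grades. SAP 8.2.3 does not mention grading.

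**The concern.** The top class has no upper bound. A subject who enters in it cannot move up, however large the later rise, so the table can register only stability or improvement for that subject. The entry criteria allow such subjects on the kidney and liver tests that the primary safety objective names.

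A shift table exists to count subjects by change in status, and it is the only laboratory display in either document that does so. A reader comparing total USB002 with total placebo, as SAP 8.1 requires, would see no upward movement among subjects with impaired kidney or liver tests at entry, whether or not there was any. The adverse event tables count some of them, but not all: "Undesirable changes in laboratory values should not be considered AEs unless they are considered symptomatic" of a condition, judged clinically significant, or in need of therapy (Protocol 6.1.1).

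**Working it through.** There is no planned figure to reproduce, since the laboratory analysis is descriptive. The check applies the stated rule to values that the entry criteria allow.

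**Step 1: which baselines can be high?** Take ULN = 1 and call a result high if it exceeds 1.

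| Test | Part 1 entry limit (Protocol 4.2) | High baselines admitted |
|---|---|---|
| ALT, AST | excluded above 3 × ULN | above 1 and up to 3 × ULN |
| Creatinine, BUN | none (limits are for Part 2 only) | any value above 1 × ULN |

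**Step 2: what does the shift table show?** Illustrative ALT or AST values, in multiples of ULN:

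| Baseline | Later value | Ratio | Cell | Counted as a shift? |
|---|---|---|---|---|
| 0.9 | 2.5 | 2.8 | normal to high | yes |
| 1.2 | 3.6 | 3.0 | high to high | no |
| 2.0 | 6.0 | 3.0 | high to high | no |
| 2.9 | 14.5 | 5.0 | high to high | no |

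The smallest rise in relative terms is the only one counted. The SAP's use of every post-baseline visit does not alter this: high to high at each visit is still no shift.

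**Step 3: what do the change-from-baseline summaries recover?** By design each cohort has 3 active subjects (SAP 4.1). With n = 3 the minimum, median and maximum are the three individual values. If the range is printed only as a width, they still follow from the other statistics: minimum + maximum = 3 × mean − median, and maximum − minimum = range. So, within an active cohort, each individual change at each visit can be read off. The last row of the table above would appear as 14.5 − 2.9 = +11.6 × ULN, in reported units. The summary does not show which changes came from a high baseline, and it does not give each subject's worst value over visits.

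**Step 4: what about the pooled groups?** If the first three cohorts were split 3:3 as designed, they hold 3 × 3 = 9 active and 9 placebo subjects. SAP Section 2 gives 3 subjects in Cohort 4 without the split by arm, so each pooled group has 9 to 12 subjects and the two sum to 21. Mean, median and range no longer recover individual values. The maximum shows the largest rise, but neither how many others worsened nor how many of them began high.

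**Step 5: does the protocol count this way elsewhere?** Yes. For QTc, Protocol 7.2.3.4 counts subjects above 450, 480 and 500 ms, and subjects whose increase from baseline exceeds 30 and 60 ms. No equivalent is specified for kidney or liver tests.

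**The case against.** The strongest reply is that nothing is hidden. In a study of 21 subjects with no inference, every result is listed, and the cohort summaries expose each active subject's change (Step 3). That stands, and it rules out the reading that worsening would go unseen. It does not supply a count, and it weakens for pooled placebo and total USB002.

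A second reply is that clinically important worsening is caught by other routes. Protocol 6.1.1 treats worsening of a pre-existing condition as an adverse event. Protocol 6.4.2 asks for immediate notice of renal failure, acute kidney injury and liver impairment in ICU patients. The DSMB sees unblinded safety data before each escalation (Protocol 3.2 and 6.6). This also stands. A reader might infer that the whole safety assessment leans toward finding no effect, but the documents support that only for one table.

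A third reply is that CTCAE grading separates degrees of high. It would, if it were tabulated; neither document specifies such a table. One might answer that grades would count abnormality at entry as toxicity, but the documents do not set out how the scale treats an abnormal baseline, so that argument cannot be used.

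A reader might also object that a subject with both a low and a high later value appears in one direction only. That follows from the protocol's most-extreme-value wording. The SAP shifts to each time point, so both directions would appear.

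**Conclusion.** The point holds as a gap in one type of display. For any subject already high on a test at entry, the shift table in both documents cannot show a rise, and no other laboratory table counts such subjects. It can concern any of the 21 enrolled subjects, on tests named in the primary safety objective. The liver limit is common to both parts; only the absence of a kidney limit is particular to Part 1.

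The size cannot be given, because neither the share of subjects high at entry nor the share who worsened is in the documents. Assuming that 20%, 30% or 50% are high on a given test, a reader could compute 1 − (1 − p)³ = 49%, 66% or 88% as the chance that an active cohort of 3 includes at least one. Those figures rest on assumed prevalence and say only that such a subject may be present, not that anyone worsened or was missed. They are not evidence of impact.

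No conclusion of the study is shown to depend on this. It is a worthwhile, low-cost improvement to the laboratory reporting.

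**What to change.** Amend SAP 8.2.3 by addendum, or add the tables to the clinical study report as additional output:

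- For ALT, AST, bilirubin, alkaline phosphatase, creatinine and BUN, tabulate the shift from baseline CTCAE v5.0 grade to worst post-baseline grade. State in the addendum how a value that is abnormal at baseline is graded.
- For any of these tests without a usable grade, count subjects by worst post-baseline multiple of their own baseline, for example at least 1.5, 2 and 3 times.
- Present both by dose cohort, for pooled placebo and for total USB002.

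The normal-range shift tables can stay as they are. The work uses data already collected and changes nothing in the conduct of the trial. The cost is some programming and a few extra tables. The added tables should be labelled as specified after enrolment stopped.

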#### **7.2.3.3. Vital Signs**

Summary statistics (mean, median, standard deviation, minimum, and maximum) and change from baseline to each scheduled study assessment for systolic and diastolic BP, HR, RR, SpO2, and body temperature will be presented by treatment group. Baseline is defined as the latest non-missing vital sign value prior to the first study drug infusion. By-patient listings of all vital signs will be presented flagging the notable values.

#### **7.2.3.4. ECG Evaluation**

Summary statistics (mean, median, standard deviation, minimum, and maximum) and change from baseline to each scheduled study assessment for all ECG parameters will be presented by treatment group. Baseline is defined as the latest non-missing value prior to the start of the first treatment infusion.

A shift table from baseline to maximum post baseline ECG result of the number and percentage of subjects with normal, clinically insignificant abnormalities and clinically significant abnormalities will be presented. The number and percentage of subjects meeting threshold criteria for QTcF and QTcB will be presented by treatment group. The threshold criteria for QTcF and QTcB interval prolongation are as follows: [International Conference on Harmonization of Technical Requirements for Registration of Pharmaceuticals for Human Use (ICH) E14]: >450 ms, >480 ms, >500 ms, and interval increases from baseline of >30 ms and >60 ms.

By-patient listings of notable abnormal changes in ECG parameters will be presented along with the overall interpretation of ECGs for Part 1 at visits 1 (0, 48, 72, 96 hrs), 5, 7, 9 and 14 and Part 2 at Days 1 and 16.

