8.2.1. Adverse Events

Only treatment emergent adverse events (TEAEs) will be summarized. Summaries will be provided by dose level cohort with all placebo groups combined. Following summaries will be provided:

- Overview of TEAEs - include the total number of TEAEs, serious TEAEs, DLT, and TEAE leading to death
- TEAEs by MedDRA System Organ Class (SOC) and Preferred Term (PT)
- TEAEs by MedDRA SOC, PT, and severity
- TEAEs by MedDRA SOC, PT, and relationship to treatment
- TEAEs by MedDRA SOC, PT, and outcome
- Serious TEAEs by MedDRA SOC, and PT
- TEAE leading to death
- DLT.

All these summaries will include the counts and frequencies of events, and of subjects who had events.

All TEAEs will be listed by subject. Serious TEAEs, TEAEs leading to death, and DLTs will be listed separately.

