8.2.4. ECG Assessments

ECG assessments (heart rate, PR interval, QRS duration, QT interval, QTcF and QTcB intervals, and overall assessments (Normal /Not clinically significant abnormal /Clinically significant abnormal) will be summarized by dose level cohort and visit.

Change of ECG values from baseline values will be summarized for all post-baseline visits.

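### The SAP leaves out, without declaring it in section 6, the protocol's QTc threshold counts, worst-value ECG and lab shifts, CTCAE lab grading, and table of TEAEs leading to treatment withdrawal

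*Protocol*

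**What the plan says.** **Protocol.** Section 7.2.3 applies to both parts, which are to be presented separately.

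- ECG (7.2.3.4): "The number and percentage of subjects meeting threshold criteria for QTcF and QTcB will be presented by treatment group". The cut-offs are QTcF and QTcB above 450, 480 and 500 ms, and increases from baseline above 30 and 60 ms. The same section adds "A shift table from baseline to maximum post baseline ECG result".
- Laboratory (7.2.3.2): for continuous parameters, normal/low/high shift tables "will be presented from baseline to the most extreme post baseline value by group and treatment group". Abnormal values are to be graded by CTCAE v5.0, and 7.2.3.1 repeats that requirement.
- Adverse events (7.2.3.1): a list described as the minimum, which the SAP may extend. It includes the number and percentage of patients "reporting a TEAE leading to withdrawal from study treatment by treatment group", preferred term and system organ class.

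**SAP.**

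- 8.2.4: ECG parameters and the overall reading are summarised by dose cohort and visit, and "Change of ECG values from baseline values will be summarized for all post-baseline visits". There are no thresholds and no shift to maximum.
- 8.2.3: for laboratory status, "The status will be summarized using shift tables from baseline to each post-baseline time point". CTCAE does not appear in the SAP text.
- 8.2.1: the TEAE overview is to "include the total number of TEAEs, serious TEAEs, DLT, and TEAE leading to death". Neither the overview nor the rest of the list covers TEAEs leading to treatment withdrawal.
- Section 6, which records changes from the protocol, has three entries: Part 2 analyses, OSCI time-to-event estimates, and vasoactive agent use.

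**The concern.** ECG and laboratory changes are named primary safety measures (Protocol 2.1.1; SAP 4.2 and 8.2), and stopping treatment because of an adverse event is a direct measure of tolerability. SAP section 2 says the trial ended with 21 subjects, all in Part 1, and SAP 7.4 rules out inference. The descriptive tables are therefore the trial's whole safety readout.

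In groups this small, the useful question is how many subjects ever reached a level of concern. QTcF above 450 ms is an exclusion criterion (Protocol 4.2), so a later QTcF above that level is normally a new finding, and the protocol planned to count it. A reader who compares the final report with the protocol would find these tables missing and no explanation.

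**Working it through.** The plan states no figure to reproduce; Protocol 7.3 says no sample size calculation was made for Part 1. The check has three steps: compare the sections, ask whether the remaining outputs can replace what is missing, and put a size on the loss.

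**1. Side by side**

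| Protocol commitment | SAP counterpart | Declared in SAP section 6? |
|---|---|---|
| QTcF/QTcB counts above 450, 480, 500 ms; increases above 30, 60 ms (7.2.3.4) | None; by-visit summaries only (8.2.4) | No |
| ECG shift to maximum result (7.2.3.4) | None; overall reading by visit (8.2.4) | No |
| Lab shift to most extreme value (7.2.3.2) | Shift to each time point (8.2.3) | No |
| CTCAE v5.0 grading of abnormal labs (7.2.3.2, 7.2.3.1) | Normal/low/high or normal/abnormal status only (8.2.3) | No |
| TEAEs leading to treatment withdrawal (7.2.3.1) | None in the list (8.2.1) | No |

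The protocol uses the per-visit shift format for categorical urinalysis; the SAP uses it for all laboratory tests. The Part 2 entry in section 6 cannot account for these gaps, because the commitments also cover Part 1.

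**2. What the SAP tables would show for one extreme value**

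Assumed QTcF values for three active subjects at one visit: 420, 420 and 505 ms.

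- Mean = (420 + 420 + 505)/3 = 448.3 ms; median 420; SD 49.1; range 420 to 505.
- The mean and median stay below 450 ms, but the maximum shows a value above 500 ms. SAP 7.4 reports the range, so the value is visible. The protocol's table would read 1/3 above 500 ms.

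Assumed changes of 0, 0 and +65 ms give a mean of 65/3 = +21.7 and a maximum of +65. Again the range shows the extreme.

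**3. What they cannot show across visits**

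Suppose the maximum QTcF exceeds 450 ms at three visits. The ranges are the same whether one subject crossed three times or three subjects crossed once each. Only a per-subject count separates 1/3 from 3/3.

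The same holds for lab status and the overall ECG reading. If three subjects are each abnormal once, all at different visits, no by-visit table exceeds 1/3, while a worst-value table reads 3/3.

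How often would the visits all differ? Inputs from Protocol 5.2 and 5.4.2:

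- ECG after baseline: 48, 72 and 96 hours, Visit 5, Days 7, 9 and 14, so V = 7.
- Labs after baseline: 24, 48, 72 and 96 hours, Visit 5, Days 14, 21 and 28, so V = 8.

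Assume one abnormal visit per subject, falling independently and uniformly over V attended visits. Then P(all different) = (V − 1)(V − 2)/V².

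- ECG: 6 × 5/49 = 0.61
- Labs: 7 × 6/64 = 0.66

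Subjects discharged early skip later site visits (Protocol 5.4.5), so by-visit denominators also shrink over time.

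**Group sizes.** Enrolment is 3 × 6 + 3 = 21. The design gives 3 active subjects in each of the first three cohorts. Cohort 4 has 3 subjects in total and its arm split is not stated, so pooled active is 3 × 3 plus 0 to 3, that is 9 to 12.

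**The case against.** The strongest reply is that nothing is lost at subject level. SAP 8.1 lists all EDC data, 8.2.3 lists all labs by subject, and 8.2.1 lists all TEAEs, with serious events, deaths and DLTs listed separately and a table by severity. SAP 7.4 reports the range. With 21 subjects, a reader can go through the listings. Escalation decisions were the DSMB's, made on unblinded data (Protocol 3.2, 6.6), so no dose decision in this trial rests on these tables.

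Much of this stands, and it rules out several stronger readings that a reader might infer:

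- *That the SAP hides single-subject toxicity, or that an outlying QTc change vanishes into a mean.* Step 2 shows that the range exposes it, and the listings do too.
- *That by-visit summaries replaced the protocol's analysis.* The protocol also asks for by-visit summaries. What is missing is the further per-subject roll-up. The TEAE tables are not by visit at all.
- *That the protocol promised a table of worst CTCAE lab grade.* It requires grading but names no such table.
- *That treatment withdrawal goes unrecorded.* SAP 8.1.4 lists the reasons for incomplete infusions and related AEs.
- *That every dose has 3 active subjects.* The Cohort 4 figures do not support this.

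Three gaps remain. Listings leave the reader to rebuild by hand counts that the protocol specified. The TEAE severity table does not stand in for lab grading, because Protocol 6.1.1 treats a lab change as an AE only if it is symptomatic, judged clinically significant or needs therapy. The early-withdrawal summary in SAP 8.1.1 need not capture stopped infusions, because Protocol 4.3 reserves study withdrawal for withdrawn consent; a subject who stops infusion for an AE stays in the study.

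**Conclusion.** The point holds as an undeclared mismatch between protocol and SAP in the primary safety tabulations. Five commitments have no counterpart in SAP 8.2.1, 8.2.3 or 8.2.4, and none is among the three changes declared in section 6.

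The practical loss is the per-subject count. By-visit ECG and lab tables can show at most 1/3 where the worst-value answer is 3/3. That pattern has probability 0.61 (ECG) or 0.66 (labs) under the assumptions in step 3: three subjects, one abnormal visit each, visits independent and equally likely, full attendance. The 3-subject example fits the planned active group in the first three cohorts and may not fit Cohort 4.

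The consequence is for the completeness and readability of the final safety report. The documents do not support a claim that toxicity is concealed or that dosing decisions were affected. The tables should be restored, because the data are primary and the cost is small.

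**What to change.** Amend the SAP as follows, with each table by dose cohort and for pooled active against combined placebo, the grouping SAP 8.1 already uses:

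- **8.2.4:** counts and percentages of subjects with any post-baseline QTcF or QTcB above 450, 480 and 500 ms, and with a maximum increase above 30 and 60 ms; and a shift from baseline to the worst post-baseline overall ECG result.
- **8.2.3:** a shift from baseline to the most extreme post-baseline value for continuous labs, alongside the by-visit shifts; and CTCAE v5.0 grades for abnormal labs, summarised or shown as a column in the listing.
- **8.2.1:** TEAEs leading to withdrawal from study treatment, by system organ class and preferred term, with a row in the overview.
- **Section 6:** declare and justify any of these that is not restored.

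The cost is a few extra tables for 21 subjects. The ECG, laboratory, AE and infusion data are already collected, and no change to trial conduct is needed.
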